Hypothesis Aim 1: Community engagement and mixed methods data will yield insights into current treatment seeking patterns and needs for AGYW and effective adaptation strategies to improve the proposed intervention.

Aim 2: Implement a pilot of the intervention and assess implementation outcomes.

The provider and staff component will consist of two groups to facilitate participation and accommodate provider/staff schedules. Four separate groups of AGYW will participate in the adolescent health club component, using a wait-list control group design. Separate groups are needed due to the group nature of the intervention activities which limits the number of people who can participate at one time. Intervention participants will be surveyed pre- and post-intervention to examine acceptability, feasibility, and uptake. Qualitative process data will also be collected and analyzed.

Hypothesis Aim 2: AGYW's satisfaction with services will improve 20% post-intervention compared to pre-intervention.

Aim 3: Assess a pilot set of health outcomes for future research.

Quantitative pre- and post-tests will also assess pilot effectiveness health and behavioral outcomes.

Hypothesis Aim 3: Sexual and reproductive health (SRH) knowledge will show statistically significant improvement post-intervention. Behavioral elements of SRH will show positive trends, but will not be statistically significant.

2. **Probable Duration of Project:** State the expected duration of the project, including all follow-up and data analysis activities.

5-6 years

3. **Background:** Describe the background information that led to the plan for this project. Provide references to support the expectation of obtaining useful scientific data.**A.1. Status of adolescent sexual and reproductive health (SRH) and adolescent-friendly health services**

Most of the over one billion people between the ages of 15-25 in the world live in low- and middle-income countries (LMICs). Among youth living in LMICs, 70% are in Asia.⁽¹⁾ Among health, education, and employment challenges facing young people, SRH need specific action.⁽²⁻⁷⁾ Adolescent girls and young women (AGYW) are particularly vulnerable with adolescent pregnancy, maternal morbidity and mortality, STIs/HIV, gender-based violence, and psychological trauma stemming from these issues given their precarious status in patriarchal cultures.⁽⁸⁻¹¹⁾ While striving to achieve the Millennium Development Goals, the global health agenda largely

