My previous work has contributed to key areas of this proposed K award. Previous work with AGYW and providers in Mumbai: Over the course of my graduate work, I spent over a year living and working in and around the study area to explore factors related to young women's age at marriage and SRH, as well as support STI/HIV risk reduction interventions. **Through this work, I developed working relationships with NGOs, research institutions, and healthcare providers working in the study area.** I presented my findings in discussions at community dissemination meetings (N=10 meetings averaging 15 participants per meeting), focusing on the service gaps that I identified in youth-friendly services in the study area. A recent return trip in January 2019 to the study area offered the opportunity to obtain support for this work, and talk to providers and Community Health Workers (CHWs) about the elements of the RKSK program currently being implemented. I learned that CHWs have been registering and tracking adolescents, and doing limited nutritional and hygiene health education with them, but work towards greater impact has stalled. The CHWs are responsible for leading the adolescent health clubs, but they lack training or a curriculum for the clubs. Providers currently see and refer AGYW, but feel that AGYW are not comfortable using local providers for "anything beyond colds." My previous work's promise towards research that can improve SRH for AGYW: In my K12, I have worked with adolescent girls (ages 14-18) and their providers (primarily physicians and nurse practitioners) in the U.S. to develop an electronic pre-appointment planning tool. **This work has provided insights into what patient-centered care means to youth seeking primary and SRH care, and approaches to effectively engage stakeholders** in such efforts. This work has also provided insights into provider characteristics that promote adolescent communication and uptake of services.

4. **Research Plan:** Summarize the study design and research procedures using non-technical language that can be readily understood by someone outside the discipline. **Be sure to distinguish between standard of care vs. research procedures when applicable, and include any flowcharts of visits specifying their individual times and lengths.** Describe the setting in which the research will take place.

The Pilot Intervention Model

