ADAPT-ITT Topical Expert, Integration, and Training Phases

Qualitative data analysis and finalization of intervention modules: Interviews and group discussions will be transcribed and translated (as needed, some KII materials will already be in English) and coded with the qualitative data analysis software, Atlas.ti.⁽¹¹²⁾ Using a framework approach with codes based on key implementation and conceptual model factors of interest, data will be coded and analyzed to identify elements of the intervention and evaluation instruments needing revision, with additional codes added as novel topics/issues arise.⁽¹¹³⁻¹¹⁶⁾ Coding will be conducted by myself and a research assistant, consulting with [name] as needed. Using the formative data, and the expertise of my mentors, I will adapt the intervention modules to the context, while making sure the key evidence-based elements are not lost. As needed, additional in-depth coding of the formative qualitative data can be conducted once rapid analysis for intervention adaptation has been completed. Once the modules have been finalized, the intervention facilitators will be trained, and the intervention implemented. The facilitators for the provider/staff intervention component will be [name] (Yale and ICMR IRBs), [name] (Tata Institute and ICMR IRBs), and [name] (an employee of the International Center for Research on Women, an NGO with research and intervention activities throughout India; TISS and ICMR IRBs). The facilitators for the AGYW health club intervention will be [name], and a female research assistant To-Be-Named (Tata Institute and ICMR IRBs). A CHW may help support some sessions, and if so, their participation will be covered by the Indian IRBs).

Intervention (the “Testing” phase of ADAPT-ITT; Research Aims 2 and 3)

Intervention Eligibility: AGYW inclusion criteria: AGYW between the ages of 15-25 years old, provide consent or assent, have been living in the study area for two years or more, and if unmarried and under the age of 18, have parental consent to participate. AGYW exclusion criteria: AGYW who are unable to give consent due to psychological or mental limitations, or, if unmarried and under the age of 18 do not have parental consent to participate. Provider/staff inclusion criteria: Providers or staff who work at a public or private facility in the study area that see an average of at least five AGYW per month for the past year.

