Study Design: Neither providers/staff or clinics can be randomized, as only a subset of the clinics/providers in the study area see enough AGYW to meet inclusion criteria, and some providers/staff who participate will work in the same clinics. Providers/staff will complete brief pre- and post-training surveys; however, the primary measures of their intervention will be derived from the AGYW’s outcomes.

For the adolescent health club component, the pilot study employs a waitlisted control group design^(117, 118) (Figure 2). In this modified version of the stepped wedge design,⁽¹¹⁹⁾ all groups receive the intervention, and participants serve as their own controls. This design utilizes a smaller sample size of AGYW and fewer facilitators, making it more feasible for a K award, while still enabling all participants to participate in the intervention. The waitlisted control design also avoids some of the

[figure not shown]

Figure 2: Wait-list design for four adolescent health club groups.

challenges associated with carryover effect that can occur in other crossover designs, as participants move unidirectionally from control to intervention.^(117, 118, 120) The adolescent health club curriculum (which takes approximately 2.5 months to complete) will be sequentially administered to four groups, each with a waitlisted control group. Individuals can be compared to themselves, and the other groups. Sequentially administering the intervention will be more feasible than administering the intervention simultaneously to separate neighborhood clusters, limiting the number of facilitators needed.

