Adolescent Health Club Component and Evaluation: Households with AGYW ages 15 to 25 will be identified by community health workers from randomly selected block sectors of the study area. Clubs will be conducted in separate neighborhood sectors, to limit contamination. Conducting club meetings near to the lanes adolescent girls live in will make it easier for them to attend. To further assess and address potential contamination, we will ask individuals to verify the adolescent health club they attended in the post-intervention survey, whether they attended an additional health club outside our intervention (such as, in school). If any contamination is evident based on this question, then we will model it. AGYW and their mothers (if unmarried and under the age of 18) will be approached by a member of the research team and the adolescent health club intervention will be explained. If consent is obtained, the AGYW will be enrolled, and randomized to either participate or join the wait-list. AGYW will complete the pre-intervention evaluation instrument upon enrollment. In addition to the activities in the "It's All One" Curriculum spread over eight modules, providers from the sensitization component will attend one meeting to discuss services available in the adolescent-friendly clinics, and hear young women's previous experiences accessing care. Similar to the process for the provider sensitization component, the facilitator will complete a log after each session to code activities as implemented fully, implemented partially or modified significantly and describe any changes. The log will also include a section to document any unusual events associated with any of the sessions, and the effect of these events on implementation, acceptability, or feasibility. Every other session will be observed and documented in fieldnotes that will be analyzed to contribute to process evaluation (see analysis details below). As with the provider component, the log and fieldnotes will enable a qualitative assessment of intervention fidelity. When young women complete the curriculum, they will also complete the post-intervention evaluation instrument. A sub-sample of young women (N=15) will be asked to participate in a focus group discussion to reflect on the club's impact and acceptability. Domains measured by previously validated instruments^(32, 48, 66, 123-126) to be covered in the pre- and post-intervention surveys are shown in Table 3. There are relatively few validated quantitative measures of implementation outcomes,^(127, 128) and none in Hindi, thus the measure we have chosen⁽¹²⁹⁾ will have to be translated and back-translated to ensure comprehension.

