The participants for the formative qualitative research (both key informants and young women) will be recruited primarily from Apnalaya's (community-based organization partnering on this study) established networks in the community over their 45 year-long work in the study area. As needed, additional recruitment will be from established networks of community leaders, NGO directors and staff, religious leaders, community health workers, and female community mobilizers. These networks have been established through the PI's previous work in the study area. Based on our previous work, we anticipate that these sources will easily yield the numbers of key informants (N=35-50) and adolescent girls and young women (N=20-70) required for the qualitative data collection in the formative stage. Mothers of girls interviewed will be asked to also participate in separate key informant interviews and theater testing groups, facilitating recruitment of this group.

For the quantitative portion of the formative research, a random sample of adolescent girls and young women (AGYW; ages 15-25 years old) seeking care at a set of public (N=3) and private (N=3) healthcare facilities in the study area will be referred by their healthcare provider and/or Apnalaya's health projects and asked to participate in a brief survey using validated measures to discuss their patterns of healthcare-seeking (where they go for different problems, and what influences those choices), and their perceptions and experiences with adolescent healthcare. Twenty to twenty- five AGYW will be surveyed from each facility, with a total N=150. Based on recent estimates of service usage, clinics in the study area see approximately 80-100 young women in the age range of 15-25 years old per month. Thus, we do not anticipate any challenges recruiting the sample size required for this quantitative survey.

Theater-testing group participants will be recruited similarly to the qualitative interviews above, and participants from the surveys may also be invited to join the theater-testing groups.

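### The Aim 2 change in satisfaction with services will mostly reflect perception rather than care received, so by itself it cannot show whether the provider training worked

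*Combined protocol and SAP*

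**What the plan says.** Hypothesis Aim 2 (Section I, 1. Statement of Purpose) is that "AGYW's satisfaction with services will improve 20% post-intervention compared to pre-intervention". The plan gives no scale, no baseline level, and no statement of whether 20% is relative or absolute. In Table 1 (Section I, 4. Research Plan) satisfaction appears only in the post-intervention column, and its object is given as either the intervention or services. Clinic uptake and use appears in both columns.

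**Who is surveyed.** "Households with AGYW ages 15 to 25 will be identified by community health workers from randomly selected block sectors of the study area". Section III, 3a assigns this step to the NGO partner's field team, but the source is still households. Eligibility is "AGYW between the ages of 15-25 years old, provide consent or assent, have been living in the study area for two years or more", plus parental consent for unmarried minors. Section I, 8 gives one year of residence, a difference that does not matter here. No section requires a clinic visit or a need for care.

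**When.** "AGYW will complete the pre-intervention evaluation instrument upon enrollment", and "When young women complete the curriculum, they will also complete the post-intervention evaluation instrument". No later survey is described. On duration: "The adolescent health club curriculum (which takes approximately 2.5 months to complete) will be sequentially administered to four groups". Under Section III, 3a each wait-listed group starts after the group before it has finished.

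**Provider component.** Section I, 4 (Study Design) and Section I, 13 both say that its primary measures will come from the young women's outcomes. Section III, 3a recruits providers and staff from the clinics used for the formative survey, three public and three private. On volume it says that "clinics in the study area see approximately 80-100 young women in the age range of 15-25 years old per month".

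**The concern.** A woman's rating of services can change through care only if she receives some between her two surveys. These women are not selected for using care, and the last survey coincides with the end of the club. If few of them are seen at a participating clinic in that time, the average change is made up almost entirely of women with no new care to rate.

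The risk is a wrong conclusion about the provider training. A rise could come from what was said in the club, from courtesy to the team, or from answering the same questions twice. No rise would not show that the training failed. The plan relies on these women's outcomes to judge that component, so either result could be misread.

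**Working it through.** **The plan's own figures.** There is no sample size for Aim 2. The only one, 50 pairs for SRH knowledge (difference 1.3, SD 3, 85% power), reproduces as a paired calculation if alpha is assumed to be two-sided 0.05: (3 x (1.960 + 1.036) / 1.3)^2 gives 48, and the exact paired t test gives 50 (power 85.2%). It does not reproduce as the two-arm comparison that the text names (96 per arm), which is a separate matter. The expected endpoint number reproduces as 100 x 0.8 = 80.

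**Inputs for the exposure check**
- Population: about 700,000 (Section I, 1).
- Women aged 15-25, W: not given, so assumed to be 5-12%, or 35,000-84,000. The upper value follows from the 60.6% under age 25 (Section I, 4) with even ages and half female: 0.606 x 10/25 x 0.5 = 0.121. Counting eleven single years gives 0.133, which would lower the visit rates further.
- Monthly volume, V: 80-100 (Section III, 3a). The text does not say whether this is a total or per clinic, so both are used: 80-100, or six times that, 480-600.
- Interval, m: about 2.5 months for group 1. For groups 2-4 it is about 5 months, one cycle waiting and one in the club.

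**Formula.** Share with at least one visit = 1 - exp(-V x m / W), at background rates and with club members assumed to be average users.

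| Reading of 80-100 a month | Per 100 women, 2.5 months | Per 100 women, 5 months |
|---|---|---|
| Total for all clinics | 0.24-0.71 | 0.48-1.42 |
| Per clinic, six clinics | 1.42-4.20 | 2.82-8.21 |

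The top corner is 600 x 5 / 35,000 = 0.0857, and 1 - exp(-0.0857) = 0.0821. The plain ratio of visits to women peaks at 4.3 per 100 over 2.5 months and 8.6 over 5 months, so the formula makes little difference. Of 80 women analysed, the range is 0.2 (2.5 months, volume a total, 84,000 women) to 6.6 (5 months, per clinic, 35,000 women).

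**What a 20% average rise would require.** Suppose that only visitors changed and that they began at the same mean as the rest. The rise needed among them is 20% divided by the share visiting. In the most generous case that is 20 / 0.082, about 240%. With 84,000 women on the same volume and interval it is 20 / 0.0351, about 570%.

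**If the club raised clinic use.** The plan gives no multiplier, so these are illustrations, applied to the whole 5 months at 600 visits a month. Threefold use gives about 18 of 80 women with 35,000 in the area, or 8 of 80 with 84,000. Fivefold gives about 28 and 13. Even at 28 of 80, about two-thirds (52 of 80) have no visit to rate.

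**The case against.** A reader might infer that almost no club member will have met a trained provider. The documents do not support that. Providers from the sensitization component attend one club meeting (Section I, 4), so every woman present meets them. Up to 20 community health workers are also trained, and such workers make door-to-door rounds with education and basic medications. What remains is that a discussion at the club is not care, and that the plan does not say whether trained workers cover the club sectors.

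A reader might also infer that Aim 2 concerns clinic services and cannot be answered at all. The hypothesis says only *services*, and Table 1 allows the intervention itself. If the club is meant, every attender is exposed. Aim 2 also covers acceptability, feasibility, uptake and qualitative process data, which this point leaves untouched. Uptake can occur during the club and is surveyed before and after.

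The visit rate is not purely the plan's own, because the number of women aged 15-25 is assumed. It also covers only six clinics in an area with other public, NGO and private providers. Visits elsewhere would be real care, though they would say little about the trained providers. For groups 2-4, a visit while waiting could affect the pre/post score, and provider training is not dated relative to the clubs. The 5-month column allows for that. The remark in Section I, A.6 that young women are uncomfortable using local providers for more than minor illness is the providers' impression, and no weight is placed on it.

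Finally, satisfaction-type items may sit within the uptake domain, which cites youth-friendliness questionnaires. The plan does not say so, and the instruments are not shown.

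**Conclusion.** The point holds in this form: an all-women pre/post change in satisfaction will mostly reflect perception, and cannot by itself show whether the provider component worked. At background rates, between 0.2 and 4.2 per 100 women would have a visit at a participating clinic over 2.5 months, and at most about 8 per 100 over 5 months.

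This rests on the assumed 35,000-84,000 women, on average use among club members, and on services meaning facility care. It survives both readings of the clinic volume and the whole population range. It does not depend on women having no contact with trained staff. Uptake caused by the club is unknown, and it would have to exceed fivefold in the most generous case before most women had a visit to rate.

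Separately, and without any assumption about visits, the stated 20% change cannot be computed from Table 1 as it stands, because satisfaction is listed only after the intervention.

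**What to change.** 1. State whether *services* in Hypothesis Aim 2 means facility care, the club, or both, and define what 20% refers to.
2. In the post-survey, record any facility visit or community health worker contact since the club began, and whether it was at a participating clinic. If the uptake items already capture this, only the reporting rule is needed. State how contact during the wait is classed for groups 2-4.
3. Report satisfaction separately for women with and without such contact, with denominators. Label the all-women score as perceived service quality, and do not attribute it to provider training.
4. Collect satisfaction at baseline as well, or drop the pre/post 20% wording.

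The cost is one or two survey items, the satisfaction items at baseline if that option is chosen, and some rewording. The downside is that the group with contact will be small and self-selected, so its results can only be descriptive. For that reason Aim 2 should not be restricted to visitors. Re-contacting women months later is not proposed either: Section IV has contact details destroyed once participation ends, so it would need a change to the confidentiality provisions.
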